5.3 CONCOMITANT MEDICATIONS

5.3.1 Required Medications

5.3.1.1 Required Immunosuppression

Participants are required to be on one of the following medications at study entry:

- Methotrexate ≤ 25 mg/week.
- Mycophenolate mofetil ≤ 3 grams/day or mycophenolate sodium ≤ 2.16 grams/day.
- Azathioprine $\leq 3 \text{mg/kg/day}$.

It is recommended that these medications are maintained at a stable dose, however dose reductions are allowed for toxicity associated with these medications or in case of infection, per investigator judgment.

5.3.1.2 Contraception

Use of two methods of medically acceptable contraception are required for participants and their partners (if of reproductive potential) during the study and for at least 6 months after last dose of study drug. Women of childbearing potential includes any female who has experienced menarche and who has not undergone successful surgical sterilization (hysterectomy, bilateral tubal ligation, or bilateral oophorectomy) or is not postmenopausal. Postmenopausal is defined as amenorrhea for 12 consecutive months without another cause, or documented follicle-stimulating hormone level > 35 mIU/mL for women with irregular menstrual periods and on hormone replacement therapy.

Acceptable forms of effective contraception include established use of oral, injected, or implanted hormonal methods of contraception; placement of an intrauterine device or intrauterine system; barrier methods of contraception (condom or occlusive cap) with spermicidal foam/gel/film/cream/suppository; male sterilization; and true abstinence. Female participants of childbearing potential taking concomitant mycophenolate and oral contraceptives must use a barrier method of contraception along with their oral contraceptives.

Mycophenolate Risk Evaluation and Mitigation Strategy (REMS). It is strongly recommended that investigators with female participants of childbearing potential taking mycophenolate mofetil enroll them in the Mycophenolate REMS program, as described in section 8.8.

5.3.2 Recommended Prophylactic Medication

Folic acid supplementation is strongly recommended for participants on methotrexate.

5.3.3 Permitted Medications

Use of hydroxychloroquine ≤ 400 mg/day is permitted at study enrollment and continuing during the study. Initiation of hydroxychloroquine during the study is not permitted.

Oral corticosteroids $\leq 10 \text{ mg/day prednisone}$ or the equivalent are permitted.

Corticosteroids may be increased for SSc or non-SSc indications on two separate occasions for a period of ≤14 days. Increases for SSc indications are not to exceed prednisone 20 mg per day or the equivalent and increases for non-SSc indications are not to exceed prednisone 0.5 mg/kg/day or the equivalent. Corticosteroid dose may be increased one time between study weeks 0 and 24 and one time between study weeks 24 and 48.

Corticosteroids are also allowed as premedication for infusion reactions, as described in section 5.1.3.4.1.

5.3.4 Prohibited Medications and Vaccines

Participants may not use immunosuppressive or immunomodulatory medications, including biologics, except those specified in the protocol. Increases above the dose at study enrollment are prohibited for the following medications:

- Methotrexate.
- Mycophenolate mofetil.
- Azathioprine.

The use of any investigational drug or investigational treatment other than those specified in the protocol is prohibited during study participation. SARS-CoV-2 vaccines and medications used for prevention and treatment of COVID-19, as authorized by the FDA for emergency use, are not prohibited.

The use of live attenuated vaccines is prohibited during treatment with study medication and for 12 weeks following treatment.

Concomitant administration of brentuximab vedotin and bleomycin is contraindicated due to pulmonary toxicity; therefore, bleomycin administration during the study is prohibited.

5.3.4.1 Special Precautions for Cytochrome P450 3A4 Inhibitors or Inducers, or P-glycoprotein Inhibitors

Concomitant use of strong Cytochrome P450 3A4 (CYP3A4) inhibitors or inducers, or P-glycoprotein (P-gp) inhibitors, has the potential to affect the exposure to MMAE. Participants who are receiving strong CYP3A4 inhibitors or inducers, or P-gp inhibitors, should be closely monitored for adverse reactions [55]. See Appendix 3 for examples [80]. These medications should be avoided, and alternatives used whenever possible.

5.4 DRUG ACCOUNTABILITY

Under federal regulations (21CFR 312.62) an investigator is responsible for delegating this responsibility to a qualified pharmacist of record (PoR) at every study site. The PoR is required to maintain adequate records of the disposition of the investigational product, including the date and quantity of drug that was received, the participants to whom drug was dispensed (participant by participant accounting), and an account of any drug accidentally or deliberately destroyed. The investigator will ensure that the investigational product supplies are stored as specified in the protocol and pharmacy manual in a secured area, with access limited to authorized study personnel as described in the clinical study agreement.

Records for receipt, storage, use, and disposition of the study drug will be maintained by the study sites. A drug-dispensing log will be kept current for each participant and will contain the identification of each participant and the date and quantity of drug dispensed. All remaining unused investigational product will be returned to the sponsor or sponsor's representative after study termination or destroyed with the permission of the sponsor in accordance with applicable law and study site procedures. If investigational product is to be destroyed locally, the investigator will provide documentation in accordance with sponsor's specifications.

All records regarding disposition of the investigational product will be available for inspection by the clinical trial monitor.

5.5 ASSESSMENT OF COMPLIANCE WITH STUDY MEDICATION

All study medications will be administered at sites by trained medical staff. Therefore, compliance will be monitored by the site and documented on the eCRF.

6. STUDY ASSESSMENTS AND WINDOWS

6.1 VISIT WINDOWS

6.1.1 Scheduled Visits

Appendix 1 presents the schedule of events for this trial. Visit 0 must occur within 28 days of Visit –1. All other scheduled study visits must occur within the time limits specified below:

Visits 1 through 8: +/-3 days

Visit 9: +/- 7 days

Visits 10 and 11: +/- 14 days

6.1.2 Window for Administration of Study Medication

The schedule for administration of study medication is described in Appendix 1. Study medication infusions must occur at least 18 days after the prior infusion.

6.1.3 Unscheduled Visits

Unscheduled visits may be performed to document any symptoms or to document a scleroderma flare during the study. Unscheduled visits may also be performed for Neurologist assessment in the event of suspected peripheral neuropathy. Assessments for an unscheduled visit are listed in Appendix 1. Some of the assessments may be omitted at the discretion of the investigator if they are not indicated.

6.2 RANDOMIZATION, BLINDING, AND UNBLINDING

6.2.1 Randomization

Participants who meet the eligibility criteria will be randomly assigned to a study treatment group, either brentuximab vedotin or placebo control. Enrollment is defined as the time of random assignment. Participants will be randomly assigned to their treatment group utilizing a centralized, automated randomization system. Randomization will not be stratified.

6.2.2 Blinding

Blinding will be maintained for all study participants and trial personnel, with the exception of the site pharmacist from the time of randomization throughout the study.

6.2.3 Unblinding

Unblinding before the study is completed will occur only if a participant's well-being is threatened and the site investigator believes unblinding is necessary to protect the participant. Unblinding may also occur in the event of pregnancy in a female participant or a male participant's partner.

Whenever possible, before treatment assignment for an individual participant is unblinded, the site investigator must confer with the NIAID medical monitor and the protocol chair. The NIAID medical monitor will notify the study management team.

If emergency unblinding is required for a subject's well-being during non-business hours, the site principal investigator or designee (i.e., sub-investigator specified on Form FDA 1572) must notify the investigative pharmacy of the need for the treatment assignment. The emergency unblinding will be recorded and reported to the DSMB. A full account of the event will be recorded, including the date and time of the emergency, the reason for the decision to unblind, and the names of the medical monitor and others who were notified of the emergency. During site visits, the site monitor must verify that the medical monitor was notified and that a written account was completed. The reasons for unblinding of a participant's treatment will be included in the final study report.

Immune Tolerance Network (ITN) and NIAID approval is required for unblinding the treatment of an individual participant or subgroups of participants for unplanned interim analyses to support DSMB reviews and final analysis.

An exception to the above rule is that Investigational New Drug (IND) Safety Reports will be reported to the health authorities, DSMB, and Institutional Review Boards (IRB) or ethics review committee in an unblinded fashion as requested by current ICH and local guidance.

6.3 GENERAL ASSESSMENTS

- Informed consent. Written informed consent will be obtained before any study assessments or procedures are performed.
- Eligibility criteria: Eligibility for study participation will be assessed during the screening period.
- Randomization.
- Demographics: age and ethnicity.
- Medical history. A history will be taken to determine if the participant has had any
 clinically significant diseases or medical procedures other than the disease under
 study.
- Scleroderma history. A history will be taken to determine the date of diagnosis of disease.
- Comprehensive physical examination.
- Limited physical examination. A physical examination focused on participant's current complaints and clinical status at the study visit will be conducted.
- Peripheral neuropathy assessment, including
 - o Pin sensibility.
 - Vibration sensibility.
 - Muscle strength.
 - o Motor symptoms (dexterity, walking, climbing, activities of daily life).
 - o Sensory symptoms (paresthesia, numbness, neuropathic pain).
 - Autonomic symptoms
- Vital signs. Weight, temperature, blood pressure, respiration, and pulse will be
 obtained at all visits. Height will be obtained at visit -1. Temperature, blood pressure,
 respiration, and pulse will be obtained immediately before study drug infusion,
 approximately every 15 minutes during the infusion, at the end of the infusion and 60
 minutes after the infusion is completed.
- Adverse events. Participants will be assessed for AEs.

 Concomitant medications. All concomitant medications and their indications will be recorded.

6.4 CLINICAL LABORATORY ASSESSMENTS

- Hematology (complete blood count, differential and platelet count).
- Serum chemistry: Blood urea nitrogen (BUN), creatinine, eGFR and liver panel (AST, ALT, alkaline phosphate, direct and total bilirubin). eGFR will be calculated according to the CKD-EPI formula [81].
- Serum amylase and lipase.
- HIV, unless test has been performed within 30 days of visit -1 and documented test results are available.
- Hepatitis B (surface antibody, core antibody, and surface antigen), unless test has been performed within 30 days of visit -1 and documented test results are available.
- Hepatitis C (RNA and antibody), unless test has been performed within 30 days of visit -1 and documented test results are available.
- Erythrocyte sedimentation rate (ESR).
- Serum Human Chorionic Gonadotropin (HCG) for women of childbearing potential (see section 5.3.1.2).
- STAT Urine Human Chorionic Gonadotropin (HCG) for women of childbearing potential (see section 5.3.1.2).
- QuantiFERON®-TB Gold or TB Gold Plus, unless test has been performed within 30 days of visit -1 and documented test results are available. (PPD tuberculin skin test may be substituted for the QuantiFERON®-TB Gold or TB Gold Plus).
- PCR test for SARS-CoV-2 within 14 days prior to enrollment.

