1.4 SUMMARY OF KNOWN AND POTENTIAL RISKS AND BENEFITS FOR HUMAN PARTICIPANTS

1.4.1 Risks

Brentuximab vedotin is associated with a number of known toxicities as summarized in the prescribing information [55]. A safety review of brentuximab vedotin for HL has been published [66]. Brentuximab vedotin has been tested and approved for relapsed or refractory HL and ALCL following at least one prior high dose multi-agent regimen of chemotherapy, and prior autologous stem cell transplant in the case of HL. As such, the adverse events described below have generally occurred in the setting of prior or concurrent high dose chemotherapy.

Adverse events occurring in greater than or equal to 10% of participants in the pivotal phase II trial in HL included peripheral sensory neuropathy, nausea, fatigue, neutropenia, diarrhea, pyrexia, vomiting, arthralgia, pruritus, myalgia, peripheral motor neuropathy, and alopecia [56]. Treatment emergent hyperglycemia has been reported at 5.4% to 12.1% across studies, with associated risk factors being pre-existing hyperglycemia and high body mass index greater than 30 kg/m² [65]. Serious events of hyperglycemia reported in people treated with brentuximab vedotin include new onset hyperglycemia, exacerbations of pre-existing diabetes mellitus, and ketoacidosis (including fatal outcomes) [65]. The prescribing information highlights specific warnings for peripheral neuropathy, anaphylaxis and infusion reactions, neutropenia, thrombocytopenia, anemia, serious and opportunistic infections, hepatotoxicity, pulmonary toxicity, gastrointestinal complications, Stevens-Johnson syndrome, toxic epidermal necrolysis, and fetal harm, with a black box warning for progressive multifocal leukoencephalopathy (PML).

Version 5.0

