8.3 GRADING AND ATTRIBUTION OF ADVERSE EVENTS

8.3.1 Grading Criteria

The study site will grade the severity of adverse events experienced by the study subjects according to the criteria set forth in the National Cancer Institute's Common Terminology Criteria for Adverse Events (CTCAE) Version 5.0 (November 27, 2017), except for the grading of liver chemistry abnormalities, which is described in Section 8.3.2. This document (referred to herein as the NCI-CTCAE manual) provides a common language to describe levels of severity, to analyze and interpret data, and to articulate the clinical significance of all adverse events.

Adverse events will be graded on a scale from 1 to 5 according to the following standards in the NCI-CTCAE manual:

Grade 1 = mild adverse event.

Grade 2 = moderate adverse event.

Grade 3 = severe and undesirable adverse event.

Grade 4 = life-threatening or disabling adverse event.

Grade 5 = death.

For grading an abnormal value or result of a clinical or laboratory evaluation (including, but not limited to, a radiograph, an ultrasound, an electrocardiogram etc.), a treatment-emergent adverse event is defined as an increase in grade from baseline or from the last post-baseline value that doesn't meet grading criteria. Changes in grade from screening to baseline will also be recorded as adverse events if related to a study-mandated procedure, treatment, or change in treatment (but are not treatment-emergent). If a specific event or result from a given clinical or laboratory evaluation is not included in the NCI-CTCAE manual, then an abnormal result would be considered an adverse event if changes in therapy or monitoring are implemented as a result of the event/result.

For additional information and a printable version of the NCI-CTCAE manual, consult the NCI-CTCAE web site:

https://ctep.cancer.gov/protocoldevelopment/electronic_applications/docs/CTCAE_v5_Q uick_Reference_8.5x11.pdf

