8.4.2 Collecting Adverse Events

Adverse events (including SAEs) may be discovered through any of these methods:

- Observing the subject.
- Interviewing the subject (e.g., using a checklist, structured questioning, diary, etc.).
- Receiving an unsolicited complaint from the subject.
- In addition, an abnormal value or result from a clinical or laboratory evaluation can also indicate an adverse event, as defined in Section 8.3.1.

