APPENDIX 1. SCHEDULE OF EVENTS

Study Week	-1	0	3	6	9	12	15	18	21	24	28	36	48	DSC	UN
Visit Number	-1	0	1	2	3	4	5	6	7	8	94	10	11		
General Assessments															
Informed consent	Х														
Eligibility criteria	Х														
Randomization		Х													
Demographics	Х														
Medical History	Х														
Scleroderma History	Х														
Comprehensive physical examination	Х									Х			Х	х	
Limited physical examination		Х	Х	Х	Х	Х	Х	Х	Х			Х			х
Peripheral neuropathy assessment	Х		Х	Х	Х	Х	Х	Х	Х	Х	X ⁵	Х	Х	х	х
Neurologist assessment ¹															X ¹
Vital signs	Х	Х	Х	Х	Х	Х	Х	Х	Х	Х		Х	Х	х	х
Adverse Events	Х	Х	Х	Х	Х	Х	Х	Х	Х	Х	Х	Х	Х	х	х
Concomitant medications	Х	Х	Х	Х	Х	Х	Х	Х	Х	Х	Х	Х	Х	х	х
		Clin	ical L	.abora	tory A	Sses	smen	ts					•		
Hematology ²	Х	Х	X ²	X ²	X ²	Х		Х	Х	Х	х				
Serum chemistry ²	Х	Х	X ²	X ²	X ²	Х		Х	Х	Х	х				
Serum amylase and lipase	Х														
HIV	Х														
HBV	Х														
HCV	Х														
ESR	Х					Х				Х			Х	Х	
Serum HCG ³	\mathbf{x}^3														
STAT Urine HCG ³		\mathbf{X}^3	X^3	X^3	\mathbf{X}^3	X^3	X ³	X^3	X^3	X^3		X^3	X ³	X ³	X ³
QuantiFERON Gold, Gold Plus or PPD	Х														
PCR test for SARS-CoV-2	Х														
		G	enera	Clini	cal As	sessi	nents								
EKG	Х														
Echocardiogram	Х									Х					
		Dis	sease	-Spec	ific A	ssess	ments	5							
Spirometry (FVC and FEV1) with DLCO ⁶	х					х				х			Х	х	
mRSS	Х	Х				Х				Х			Х	х	
Physician global assessment		Х								Х			Х	Х	
Patient global assessment, PROMIS- 29, SHAQ-DI		х								Х			Х	Х	
			St	udy N	ledica	itions									
Study medication administration		Х	Х	Х	Х	Х	Х	Х	Х						
Mechanistic Assessments															
Skin biopsy		Х				Х				Х					
Plasma/Serum assays		Х				Х				Х			Х	Х	
PBMC assays		Х				Х				Х			Х	Х	
Whole blood DNA genotyping		Х													
Whole blood gene expression analysis		Х				Х				Х			Х	Х	

Version 5.0

¹ As indicated for suspected peripheral neuropathy
² Hematology and serum chemistry results must be obtained within 72 hours prior to infusions at weeks 3 through 21
³ For women of childbearing potential (see section 5.3.1.2)

⁴ Visit 9 will be conducted remotely except if the participant is being followed for a peripheral neuropathy adverse event.
⁵ Performed only if the participant is being followed for a peripheral neuropathy adverse event.
⁶ Negative SARS-CoV-2 test maybe required prior to PFTs per institutional guidelines.

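### Hyperglycemia is a named risk of the study drug in 1.4.1, but no glucose value is required at screening, baseline or on treatment, so asymptomatic elevations are not systematically ascertained

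*Protocol*

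**What the plan says.** Protocol section 1.4.1 (Risks) states: "Treatment emergent hyperglycemia has been reported at 5.4% to 12.1% across studies". It names the "associated risk factors being pre-existing hyperglycemia and high body mass index greater than 30" kg/m². On severity it says: "Serious events of hyperglycemia reported in people treated with brentuximab vedotin include new onset hyperglycemia". The same sentence goes on to exacerbations of existing diabetes and to ketoacidosis, with fatal outcomes. The section also cautions that "the adverse events described below have generally occurred in the setting of prior or concurrent high dose chemotherapy".

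Section 6.4 lists the laboratory tests. The chemistry entry reads: "Serum chemistry: Blood urea nitrogen (BUN), creatinine, eGFR and liver panel (AST, ALT, alkaline phosphate, direct and total bilirubin"). Appendix 1 schedules that panel at screening and at Visit 0, and its footnote adds: "Hematology and serum chemistry results must be obtained within 72 hours prior to infusions at weeks 3 through 21".

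On how laboratory events are found, section 8.4.2 says: "an abnormal value or result from a clinical or laboratory evaluation can also indicate an adverse event, as defined in Section 8.3.1". Section 8.3.1 supplies the rule for graded results: a "treatment-emergent adverse event is defined as an increase in grade from baseline or from the last post-baseline value that doesn't meet grading criteria".

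**The concern.** The primary objective is safety and tolerability, and hyperglycemia is one of the few risks for which 1.4.1 gives an incidence range together with fatal reports. The panel in 6.4 is written out analyte by analyte, so a site that follows it exactly never measures glucose. A laboratory finding can become an adverse event only if someone takes the measurement, and a statistical analysis plan cannot recover values that were never obtained.

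The protocol tests for less frequent risks. Section 1.4.1.3 puts hepatobiliary disorder below 2%, and liver tests are required before each infusion from week 3. It puts acute pancreatitis in clinical trials at no more than 0.3%, and amylase and lipase are measured at screening. Incidence is not the only reason to monitor, but the contrast makes the absence of glucose hard to explain.

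Two uses of the data are at stake. The Safety Review Committee must approve each escalation after the 12-week review (8.11.2), and laboratory values are among the measures for that review (9.2.6, 9.2.7). The committee would have no protocol-required glucose data by dose or against placebo. In addition, a single glucose value found on treatment may have neither of the comparators that 8.3.1 uses.

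**Working it through.** **Where a glucose value could be required**

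- Section 6.4: BUN, creatinine, eGFR, AST, ALT, alkaline phosphatase, direct and total bilirubin, with amylase and lipase as a separate entry. No glucose.
- Appendix 1: rows for hematology, serum chemistry, amylase and lipase, HIV, HBV, HCV, ESR, HCG, tuberculosis and SARS-CoV-2. None for glucose, HbA1c or urinalysis.
- Section 4.2, laboratory exclusions: neutrophils, platelets, hemoglobin, liver tests, bilirubin, amylase and lipase. No glucose limit.
- Sections 5.2.4 and 8.5.2: hyperglycemia is neither a listed toxicity criterion nor an event of special interest.

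No section requires a glucose value at any visit.

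**Whether eligibility removes the risk factors named in 1.4.1**

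- Pre-existing hyperglycemia is excluded only as a confirmed diagnosis of diabetes mellitus, so undiagnosed hyperglycemia can pass screening unseen.
- Body mass index is not limited, and 5.1.3.1 provides for participants above 100 kg.

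The risk factors are covered only in part.

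**Which cases are still captured**

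- Symptomatic cases: AE assessment at every visit (8.4.2, Appendix 1).
- Serious cases: SAE reporting within one business day (8.5.2).
- Asymptomatic cases: only if a site or an outside provider tests glucose, or if AE interview or the concomitant-medication record (6.3) brings the finding to light.

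**The plan's own detection arithmetic**

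Table 2 in section 9.3 uses 1 − (1 − p)^n. For n = 6 and p = 0.1 this gives 1 − 0.9^6 = 0.469, which matches the stated 0.47. The formula gives the chance that an event occurs. It equals the chance of observing one only if events that occur are ascertained.

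**Scale, for illustration only**

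Inputs: 3 cohorts × 6 active = 18 active participants (9.3), and rates of 5.4% and 12.1% (1.4.1, given without grade). Assumption: the rates carry over unchanged to this population, these doses and this duration.

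- Lower rate: 18 × 0.054 = 0.97 expected cases
- Upper rate: 18 × 0.121 = 2.18 expected cases

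These counts include cases that symptoms would reveal.

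**Draws already in place**

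Chemistry is required before the infusions at weeks 3, 6, 9, 12, 15, 18 and 21, which is 7 draws, in addition to screening and Visit 0.

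**The case against.** The strongest reply is that nothing here is misstated. Section 1.4.1 is a background summary that lists many toxicities and commits the trial to no particular test for each. Which analytes to schedule is a design choice. That stands. A reader might infer that 1.4.1, 6.4 and Appendix 1 contradict one another, but they do not, because the protocol never promises glucose monitoring.

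A second reply is that asymptomatic elevations have other routes into the data. Participants are interviewed for adverse events, and concomitant medications with their indications are recorded, at every scheduled visit. A glucose result from outside care or a newly started glucose-lowering drug could surface that way. This also stands, and it rules out the claim that such cases are found only when a site chooses to measure glucose. What remains is that these routes are incidental and may differ between sites.

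Third, a reader might infer that the Grade 2+ and Grade 3+ proportions are biased downward. The document does not show this. Apart from SARS-CoV-2 infection, only Grade 2 or higher events go on the AE eCRF (8.4.3), and the primary endpoint needs Grade 3 or higher. Grading follows CTCAE version 5.0, whose hyperglycemia criteria are not reproduced, and 1.4.1 gives no rate by grade.

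Fourth, one could compute the chance of at least one case among 18 active participants as 1 − 0.946^18 = 0.63 to 1 − 0.879^18 = 0.90 and read it as the chance of a missed case. It is not that. It counts cases with and without symptoms, and the document does not give the silent share. Nor are the expected counts upper limits. Section 4.5 allows up to 8 extra participants in a cohort, and permitted corticosteroids (5.3.3) could raise the rate. The diabetes exclusion and the lower doses in two of the three cohorts could reduce it.

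The comparator argument is also limited: a site with an earlier on-treatment value that does not meet grading criteria can apply 8.3.1 as written.

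**Conclusion.** The point holds as a gap in safety ascertainment that is worth considering. Confidence is high that the protocol requires no glucose value at screening, baseline or on treatment, while itself reporting hyperglycemia at 5.4% to 12.1% with serious and fatal events. Confidence does not extend to the size of the consequence.

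The only figure available is illustrative: about 1.0 to 2.2 cases among 18 active participants. It assumes that rates seen largely with prior or concurrent high-dose chemotherapy apply unchanged to a trial that excludes diagnosed diabetes and plans 12 of its 18 active participants below 1.8 mg/kg. The number of silent cases, and any effect on a graded endpoint, cannot be derived from the document.

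**What to change.** Add glucose to the serum chemistry analytes in 6.4, measured at screening/baseline and at the existing chemistry draws in Appendix 1. Values would then be available by dose and against placebo for the Safety Review Committee, the 8.3.1 rule would have a comparator, and ascertainment would not depend on site practice.

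The cost is one analyte on blood already drawn and one eCRF field. The downside is that some non-fasting or corticosteroid-related elevations will be recorded. Measuring glucose in both arms would help to interpret them. No dosing, treatment or stopping rule is proposed.
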